6.2.5 Planning and administration of external beam radiation therapy

Initial planning CTs for radiation therapy will be performed just prior to initiation of therapy. After each samarium infusion, if tolerable, the patient will be placed in a reproducible treatment position using an appropriate immobilization device based on treatment site while data from SPECT/CT is obtained. Alternatively, the two CT

components will be co-registered and combined fields generated. Subsequent radiation therapy will be planned to reach a total minimum dose to tumor of 75 Gy as described (25). The dose of supplemental EBRT will be decided after determination of the EBRT dose equivalent delivered by the ^{153}Sm in order to reach a total minimum dose to the gross tumor volume (GTV) of 75 Gy. GTV will be defined as gross tumor on the two planning CT scans. A margin of 1.5 cm will be added to the GTV to create a clinical target volume (CTV) which will be modified to exclude adjacent normal tissues that are not involved by tumor. An additional margin of 5 mm-1 cm will be placed around the CTV to create a planning target volume (PTV) and will be dependent on treatment site and immobilization technique.

Conformal techniques such as intensity-modulated radiotherapy (IMRT) or tomotherapy will be used to plan the supplemental EBRT. The goal will be to achieve a target supplemental EBRT dose coverage of $D_{95} > 95\%$ to the PTV. Normal tissue dose constraints based on QUANTEC will be applied and respected. Standard protocols apply for supportive care based on site irradiated, and toxicity will be closely documented.

6.3 ON-STUDY EVALUATION

- 6.3.1 Dosimetric studies by ^{153}Sm SPECT/CT to be assessed at approximately 4, 24, and 48 hours after injection of tracer dose of ^{153}Sm -EDTMP; SPECT/CT will also be collected at approximately 4, 24, and 48 hours following the therapeutic administration of ^{153}Sm -EDTMP. Scans can be obtained at any time on the first and second day after infusion of ^{153}Sm -EDTMP, as long as the specific number of hours post-infusion is recorded.
- 6.3.2 Complete evaluation, including history and physical exam, vital signs, weights, and laboratory evaluation including complete blood counts and a complete metabolic panel, Mg and Phosphorous to be performed weekly until hematopoietic recovery and until recovery from therapy-related toxicities.
- 6.3.3 Because of the risk of renal and bladder toxicity from the excretion of ^{153}Sm -EDTMP that is not adsorbed to tumor, care will be taken to monitor patients closely for urinary tract toxicity. Prior to treatment, patients will have a complete urinalysis, measurement of BUN and creatinine, and 24- hour urine collection for creatinine clearance. These tests will be repeated as clinically indicated based on urinary symptoms and at the completion of therapy.
- 6.3.4 Restaging evaluation to include radiologic imaging by CT or MRI of the primary tumor and metastases, follow up [^{18}F]-MISO/[^{18}F]-FDG PET, plain radiographs of primary lesion, and Tc-99m bone scan. These studies will occur approximately one month after completion of external beam radiotherapy. Based on our prior experience with [^{18}F]-FDG PET and the lack of correlation between clinical response and SUV levels, we will not use [^{18}F]-MISO/[^{18}F]-FDG PET SUVmax measurements to determine clinical response while the patient is receiving treatment.

- 6.3.5 CT scan of chest and Tc-99m bone scan every 4 months after completion of therapy for one year, then every 6 months for 1 year, and then yearly for 3 years. Thereafter scans will be repeated only as clinically indicated.
- 6.3.6 Evaluation for long-term skeletal toxicity will be performed every 6 months for the first 4 years after completion of therapy, and will include alkaline phosphatase and LDH (bone fractions), serum C-telopeptide and parathyroid hormone levels, and bone density scans.
- 6.3.7 If any lesions are resected after patient has completed radiation therapy, percent necrosis will be determined by the pathologist and recorded.

6.4 Schedule of Assessments

Table 1. Schedule for On-Study Patient Evaluations.

(Note this does not include additional clinically appropriate testing in the setting of stem cell rescue and routine monitoring while on external beam radiation therapy.)

Evaluation	PreTx ¹	1 st Sm	2 nd Sm	External Beam Radiation				
	Week	1	2	3	4	5	>	
1 st Day of Week	-3- 0	1	8	15	22	24	29	
H&P, Vital signs and Wt	x	x	x	X ³	x		x	
Ht and BSA (baseline only)	x							
CBC	x		x	x ³	x		x	
CMP	x		x	x ³	x		x	
Ca/Phosphorus/Mg	x		x	x	x		x	
Alk Phos ⁴ , LDH ⁴	x							
C-telopeptides (JHH Path test code 6315) + PTH	x							
Ionized Ca level ⁵		x	x					
Urinalysis	x							
Creatinine Clearance ⁶	x							
Hematopoietic stem cell (HSC) collection ⁷	x							
EKG ⁸	x	x	x					
Chest X-ray	x							
CaCO ₃ (oral)		X ⁹	X ⁹					
Mycotic disease prophylaxis ¹⁰ (oral)		x	x	x	x	x	x	
Pneumocystis carinii pneumonia prophylaxis ¹¹ (oral)		x	x	x	x	x	x	
Stem Cell Infusion						x		
Rad Onc Planning CT	x ¹²							
¹⁵³ Sm planar imaging of abdomen			x ¹³					
SPECT/CT		X ¹⁴	X ¹⁴					
CT/MRI ¹⁵	x							
CT chest								
^{99m} Tc-Bone Scan	x							
Plain radiographs of primary lesion	no							
¹⁸ F-FDG PET/CT	x							
¹⁸ F-MISO PET	x							

- Table 1 Footnotes: ¹ Pre-treatment radiographic evaluation must be obtained within 3 weeks of study entry. Pre-treatment laboratory studies must be obtained within 2 weeks of study entry. Blood tests need not be repeated prior to first ¹⁵³Sm-EDTMP treatment.
- ² Start between D15 and D22
- ³ Weekly H&P, labs til CBC and AE recovery
- ⁴ Alk phosphatase and LDH will be fractionated if elevated. (Quest lab referral tests)
- ⁵ Check prior to administration of ¹⁵³Sm-EDTMP
- ⁶ Measured creatinine clearance or nuclear medicine GFR. Do not use calculated creatinine clearance.
- ⁷ Ifos + Mesna x 5 days recommended. Peripheral CD-34 cell count done daily starting at chemo D7 until high enough for pheresis.
- ⁸ Obtain at screening, pre and at completion of ¹⁵³Sm-EDTMP infusions on Days 1 and 8.
- ⁹ CaCO₃ to be administered prior to ¹⁵³Sm-EDTMP; 1000 mg calcium carbonate the morning of each samarium infusion
- ¹⁰ Days 1-75
- ¹¹ From Day 1 until 6 months after completion of therapy
- ¹² Timing of Rad Onc Planning CT relative to study entry at discretion of treating physician, and coordinated by Radiation Oncology.
- ¹³ ¹⁵³Sm planar imaging of the abdomen will be performed at 1 and 2 hours after the “treatment” infusion.
- ¹⁴ SPECT/CT scans to be obtained after ¹⁵³Sm-EDTMP infusions at approximately 4, 24, and 48 hrs post each injection of ¹⁵³Sm-EDTMP. The 24 and 48 hour post- infusion SPECT/CT scans can be obtained any time one and two days after treatment, as long as the specific number of hours post-infusion is recorded.
- ¹⁵ Choice of imaging modality and location as clinically indicated. To include primary tumor and any large metastases.
- ¹⁶ Four tubes of venous blood drawn 5 minutes apart; drawn only in conjunction with FMISO PET scans, and are to be processed by nuclear medicine as a part of that scan protocol.

Table 2. Schedule for Post Treatment and Follow Up Patient Evaluations

Evaluation	Post Tx Assessment (30 days after final tx)	Months post End				
		4	6	8	12	18
H&P, Vital signs and Wt	X	X	X	X	X	X
CBC ¹	X	X	X	X	X	X
CMP ¹	X	X	X	X	X	X
Phosphorus, Mg	X	X	X	X	X	X
Alk Phos ² , LDH ²	X		X		X	X
C-telopeptides (JHH Path test code 6315)	X		X		X	X
PTH	X		X		X	X
Bone density scan			X		X	X
Urinalysis	X					
Creatinine Clearance ³	X		X		X	X
Chest X-ray		X		X	X	X
Mycotic disease prophylaxis ⁴	X (thru D75)					
Prophylaxis for Pneumocystis carinii pneumonia (PCP) ⁵	X	X	X			
CT/MRI ⁶	X	X		X	X	X
CT chest		X		X	X	X
^{99m} Tc-Bone Scan	X	X		X	X	X
Plain radiographs of primary lesion	X					
¹⁸ F-FDG PET/CT	X			X	X	
¹⁸ F-MISO PET	X			X	X	
Blood samples with F-MISO PET ⁷	X			X	X	

¹ly H&P, labs til CBC and AE recovery

² Alk phosphatase and LDH will be fractionated if elevated. (Quest lab referral tests)

³ Measured or nuclear medicine GFR

⁴ Days 1-75

⁵ From Day 1 until 6 months after completion of therapy.

⁶ Choice of imaging modality and location as clinically indicated. To include primary tumor and any large metastases.

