6.0 TREATMENT PLAN

6.1 PRETREATMENT EVALUATION

6.1.1 History and physical examination, including symptoms, height, weight, and body surface area

6.1.2 Laboratory evaluation, including CBC with differential and platelet count, comprehensive metabolic panel, urinalysis, 24-hour urine for creatinine clearance, phosphorus, magnesium, LDH, serum C-telopeptides (JHH Pathology test code 6315) and parathyroid hormone. Alkaline phosphatase and LDH will be fractionated if elevated to determine the contribution of bone isoforms (Quest referral tests).

6.1.3 Radiographic evaluation: chest X-ray, Tc-99m bone scan, and other imaging that may include CT, MRI, and/or PET/CT scans of primary tumor and any large metastases.

6.1.4 Cardiac evaluation: baseline EKG to be obtained prior to treatment.

6.1.5 As part of the study protocol, subjects will undergo a pre-treatment [¹⁸F]-MISO/[¹⁸F]-FDG whole body PET scanning as delineated in section 6.2.4.

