6.2 OVERALL TREATMENT PLAN

This is a treatment protocol to establish the safety and efficacy of radiation therapy consisting of high-dose ^{153}Sm -EDTMP and external beam radiotherapy for the treatment of high-risk osteogenic sarcoma and solid tumors with bony metastases. The primary endpoint will be clinical response of tumor lesions, defined as either stable disease or decrease in the size of the tumor by radiographic imaging (which may include CT or MRI) using RECIST 1.1 criteria. Progression will be defined as appearance of new lesions or expansion of current lesions by 20% as per RECIST 1.1 criteria. In some patients, additional information on clinical response may be obtained from histology (percent tumor necrosis) in cases where patients proceed to resection or biopsy following radiation therapy. Other treatment endpoints include progression-free and overall survival. We will obtain post-treatment [^{18}F]-MISO and [^{18}F] FDG PET scans to be analyzed but these images will not be used to define clinical response.

The first administered activity of ^{153}Sm -EDTMP will be a low “tracer” infusion administered at 1 mCi/kg on Day 1. Using the 3-dimensional dosimetry package 3D-RD, we will perform three-dimensional dosimetry using SPECT images after administration of the “tracer” activity to determine the distribution of dose delivered to the tumor and the surrounding normal tissues. As quickly as feasible (goal is within seven days), using the dosimetric results from the tracer administration, a combined treatment plan will be designed aimed at delivering the target dose to the entire tumor. This plan will be designed using methodology uniquely available at Hopkins (3D-RD software); we will import the 3-dimensional absorbed dose map resulting from ^{153}Sm -EDTMP therapy, adjusted to correspond to the fractionation schedule used in external beam radiotherapy, into the external beam planning system (Pinnacle), by fusing (registering) the SPECT/CT and absorbed dose map with the external beam planning CT, allowing a treatment plan to be generated from the combination of (1) scaling of the tracer absorbed dose map to the requisite ^{153}Sm therapeutic activity and (2) external beam fields designed to optimally complement the radiopharmaceutical absorbed dose map to deliver a target of 75 Gy to each and every tumor voxel while respecting normal organ constraints (25).

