10.0 SERIAL MEASUREMENTS (see Table 1 in Section 6.3)

- 10.1 Time of entry into the study: ^{99m}Tc bone scan, X-rays and/or CT or MRI evaluation of the primary and metastatic lesions (specific modality at clinician's discretion). A pre-treatment [^{18}F]-MISO/ [^{18}F]-FDG PET scan will be obtained for baseline readings as part of study.
- 10.2 One month after completion of external beam radiotherapy: repeat initial imaging modality and territories, as well as any other imaging clinically indicated. [^{18}F]-MISO/ [^{18}F]-FDG PET will be obtained at that time as well.
- 10.3 Subsequent follow up as per Table 1. Scans will be repeated every 4 months for the first year after completion of therapy, every 6 months during the second year after therapy, and yearly thereafter for a total of 5 years.
- 10.4 At progression, patient will undergo repeat [^{18}F]-MISO/[^{18}F]-FDG PET.

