11.2 STUDY DESIGN

This is a single-arm study with 2 strata: Stratum 1 for patients with osteosarcoma, and Stratum 2 for patients with other high risk solid tumors. Stratum 2 is exploratory in nature, and the goal of including these patients is to facilitate accomplishing secondary objectives related to toxicity and the feasibility of administering this treatment regimen to solid tumor patients. If possible, we will, however, use patients on Stratum 2 to estimate response rates of tumors other than osteosarcoma. For Stratum 1, 6-month PFS as the primary endpoint. The study will pre-specify target lesions for each patient in Stratum 1 that will be used to assess PFS, with the intention that every lesion radiographically evident at the time of enrollment will be a target lesion. Events will be the first disease progression at any of the target lesions or death from any cause. All patients treated on Stratum 1 will be included in the determination of PFS, regardless of treatment modification or discontinuation. The design will include interim analyses for futility if it seems unlikely that the treatment has sufficient activity. The historical PFS in 11 patients treated with ¹⁵³Sm-EDTMP similar to how we are proposing, but without the external beam component, was 15.8%. For this study of ¹⁵³Sm-EDTMP plus external beam radiation therapy, a 6-month PFS of 35% would be the lowest that would be considered acceptable, and PFS that is convincingly worse than this would be considered grounds for discontinuing further study. The non-parametric Kaplan-Meier estimate will be used to monitor the PFS function. After 8 patients have been enrolled, the design will include an interim analysis for futility that could halt the trial if it seems likely that this regimen does not have sufficient clinical activity. The study is designed to stop if we are 80% certain that the 6-month PFS is below 15%.

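### The primary PFS counts progression at every lesion evident at enrolment, but the imaging rules do not consistently require each of those lesions to be measured by CT or MRI

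*Combined protocol and SAP*

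**What the plan says.** For Stratum 1, Section 11.2 pre-specifies target lesions "with the intention that every lesion radiographically evident at the time of enrollment will be a target lesion". It continues: "Events will be the first disease progression at any of the target lesions or death from any cause". Section 6.2 supplies the size rule: "Progression will be defined as appearance of new lesions or expansion of current lesions by 20% as per RECIST 1.1 criteria".

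The imaging provisions are spread over several places:

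- **Baseline, Section 6.1.3:** chest X-ray, bone scan and "other imaging that may include CT, MRI, and/or PET/CT scans of primary tumor and any large metastases".
- **Baseline, Section 10.1:** "X-rays and/or CT or MRI evaluation of the primary and metastatic lesions (specific modality at clinician's discretion".
- **Schedule tables (Section 6.4), Table 1 footnote 15 and Table 2 footnote 6:** "Choice of imaging modality and location as clinically indicated. To include primary tumor and any large metastases". No size cut-off is given for *large*.
- **One month after external beam therapy, Section 6.3.4:** CT or MRI of the primary and the metastases, with no size limit. Section 10.2 has the same visit repeat the modality and territories used at baseline.
- **Later follow-up, Section 6.3.5:** "CT scan of chest and Tc-99m bone scan every 4 months after completion of therapy for one year", then less often. Table 2 nevertheless carries a CT/MRI row, separate from chest CT, at months 4, 8, 12 and 18, governed by footnote 6. Section 10.3 gives a scan calendar without saying which scans.

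Section 6.2 also says that the post-treatment PET images do not define clinical response.

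**The concern.** A 20% expansion can be called only for a lesion that has a measured baseline and a comparable later measurement. The target list is as wide as it can be, while the CT/MRI minimum in Section 6.1.3 and both footnotes is narrower and left to clinical judgement. A target outside that minimum can grow without an event being recorded.

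This is a single-arm study judged against a fixed 15.8%, so no concurrent control arm shares the under-ascertainment. A missed progression counts in favour of the regimen. The lesion-level dose-response model in Section 11.3.4 and the local control rate listed in Section 11.1 depend on the same measurements.

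**Working it through.** **1. The plan's own figures.** Section 11.3.1 gives a null 6-month PFS of 15.8%, a benchmark of 35%, exponential PFS, N = 20, one-sided alpha 0.05 and 82% power.

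- Null hazard: −ln(0.158)/6 = 0.3075 per month; median ln 2/0.3075 = 2.25 months.
- Alternative hazard: −ln(0.35)/6 = 0.1750 per month; ratio 0.3075/0.1750 = 1.76.
- Exact one-sample exponential test with 20 events: power = P(χ² on 40 df > its 95th percentile / 1.758) = 82.2%.

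The stated 82% is reproduced. The sample-size statement is not in question.

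**2. The provisions side by side.**

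| Time | Narrower rule | Wider rule |
|---|---|---|
| Baseline | 6.1.3 and footnote 15: primary and large metastases, with CT/MRI optional in 6.1.3; 10.1: X-ray alone allowed | 10.1: primary and metastatic lesions, no size limit; 11.2: all evident lesions are targets |
| One month | Footnote 6: primary and large metastases | 6.3.4: primary and metastases by CT or MRI, no size limit; 10.2: baseline modality and territories |
| Month 4 onward | 6.3.5: chest CT and bone scan; footnote 6 on the CT/MRI row: primary and large metastases | None |

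Two gaps remain once the wider rules are given full weight. First, Section 10.2 repeats whatever was done at baseline, so a target without a baseline CT or MRI is not secured by it. Section 6.3.4 would give that target a CT or MRI at one month, but with nothing comparable before it. Second, after the one-month scan no provision requires a small target outside the chest to be measured. A bone scan surveys the skeleton but does not give the dimension that the 20% rule needs.

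**3. Possible size.** The documents do not say what share of progressions would occur only in unmeasured targets. Let m be the share of true failures by 6 months that are not documented by then. This m is an assumption. With a true PFS of 15.8%, the true failure proportion is 0.842 and

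apparent PFS = 1 − 0.842 × (1 − m).

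The last column is the chance that the nominal 5% test in step 1 rejects the null, using the hazard implied by the apparent 6-month value. For m = 10% that hazard is −ln(0.242)/6 = 0.236, or 0.77 of the null hazard.

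| m (assumed) | Apparent 6-month PFS | Chance of rejecting a true null |
|---|---|---|
| 0 | 15.8% | 5% |
| 5% | 1 − 0.842 × 0.95 = 20.0% | 16.5% |
| 10% | 1 − 0.842 × 0.90 = 24.2% | 35.0% |
| 15% | 1 − 0.842 × 0.85 = 28.4% | 56.0% |
| 20% | 1 − 0.842 × 0.80 = 32.6% | 74.3% |

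The 35% benchmark is reached at m = 1 − 0.65/0.842 = 22.8%. The last column also assumes that the apparent PFS stays exponential with 20 events.

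**The case against.** The strongest reply is that the protocol does require the scan that matters most. Section 6.3.4 covers metastases of any size at one month, and Section 10.2 fixes modality and territory for that visit. PFS runs from registration (Section 11.3.5), and external beam therapy starts on Days 15 to 22 (Section 6.2). Its duration is not stated. If it is assumed to last 5 to 7 weeks, with Day 1 at registration, it ends around Days 50 to 71. The month-4 visit, about 122 days later, then falls around Days 172 to 193, on either side of 6 months. Hence at most one later scan can bear on the 6-month figure. This stands, and it limits the likely size of m. It does not remove the conflict, because footnote 6 governs the same one-month visit with a narrower scope. Later scans also feed the overall hazard estimate planned in Section 11.3.1.

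Other points stand in part. The footnotes set a minimum, not a ceiling. Chest CT shows thoracic lesions of any size from month 4. A bone scan may prompt CT or MRI. Lesions irradiated under Section 6.2.5 have a planning CT, although the protocol does not name it as the response baseline. How the 15.8% reference was imaged is not stated, so similar practice there would offset some bias. Changes of modality could also create false progressions, which would lower PFS.

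A reader might infer that most targets would never be re-measured, or that PFS is shown to be inflated. Section 6.3.4 and the CT/MRI row of Table 2 contradict the first, and nothing in the documents establishes the second. A reader might also multiply the 80% local control in Section 11.3.4 across lesions: 0.8⁴ = 41% if four targets are followed against 0.8² = 64% if only two are, a gap of 23 points. That does not hold as an estimate. The 80% is expected at 80 to 100 Gy, whereas the plan targets 75 Gy, and no time horizon is given. The lesion counts are invented, independence sits badly with the patient random effect in the same section, and deaths are left out.

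**Conclusion.** The protocol's imaging provisions conflict with each other and with the target-lesion definition behind the primary endpoint. Targets without a CT/MRI baseline, and small targets outside the chest after the one-month scan, are not reliably covered.

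Missed progressions would push the observed 6-month PFS upwards against 15.8%. This is a risk of unknown size, not a demonstrated inflation. The 20.0% to 32.6% range for m between 5% and 20% shows sensitivity only. If the sites follow Sections 6.3.4 and 10.2 with a full CT/MRI baseline, m may be close to zero and the effect negligible. The point merits correction because small values of m already move the error rate materially and the remedy is cheap.

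**What to change.** Reconcile Sections 6.1.3, 6.3.5 and 10.1 and both table footnotes with Sections 6.3.4, 10.2 and 11.2 by using one sentence throughout: *CT or MRI of every pre-specified target lesion, by the same modality as at baseline, at baseline and at every scheduled CT/MRI tumour assessment; other sites as clinically indicated.* In Section 10.1 this means that X-ray alone no longer serves as the baseline of a target lesion.

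Do not solve the problem by taking small or awkward lesions off the target list. Their progression would then drop out of the target-lesion event, which is the same under-ascertainment by another route, and it would depart from the intention in Section 11.2.

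The change is to wording only, since Table 2 already schedules CT/MRI at one month and at months 4, 8, 12 and 18. The cost is a wider scan field for some patients with scattered small metastases, and possibly a lower observed PFS.

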6.5 SUPPORTIVE CARE GUIDELINES

6.5.1 ^{153}Sm -EDTMP infusions

- 6.5.1.1 Stable central venous access is required, preferably through the placement of a double-lumen central venous catheter. Intravenous fluids will be administered to assure line patency pre ^{153}Sm -EDTMP administration and to thoroughly flush line post ^{153}Sm -EDTMP administration.
- 6.5.1.2 Administration of ^{153}Sm -EDTMP will be performed under the direction of the institution's Radiation Oncology Department/Division, according to standard procedures for the delivery of radioactive isotopes. Medical Physics personnel will be present for the entire procedure. The appropriate dose will be removed from the supplier's vial with a protected syringe and will be administered over 1-2 minutes followed by flushing of IV line to ensure line is cleared of samarium. Isolating patient and shielding from radioactivity is not necessary for ^{153}Sm -EDTMP administration.
- 6.5.1.3 Patients will take 1000 mg calcium carbonate the morning of samarium infusion to decrease the risk of transient samarium-related hypocalcemia. Ionized calcium level will be checked prior to administration of the ^{153}Sm -EDTMP. Additional calcium gluconate may be given as needed for ionized calcium less than 1.2 mmol/L. Calcium gluconate will be available for treatment of symptomatic hypocalcemia.
- 6.5.1.4 A 12-lead EKG will be checked prior to administration of ^{153}Sm -EDTMP. A second 12-lead EKG will be checked at the completion of the infusion. If any EKG changes are noted or patients develop symptoms attributable to hypocalcemia, patients may be discharged with additional calcium carbonate and arrangements made for recheck of calcium levels the following day.

